## 1. Trial Summary

### 1.1 Title

**Crystalloids Liberal Or Vasopressors Early Resuscitation in Sepsis (CLOVERS)**

### 1.2 Objective

**Primary Objective:** To determine the impact of a restrictive fluids strategy (vasopressors first followed by rescue fluids) as compared to a liberal fluid strategy (fluids first followed by rescue vasopressors) on 90-day in-hospital mortality in patients with sepsis-induced hypotension.

### 1.3 Hypothesis

**Primary Hypothesis:** Restrictive (vs liberal) fluid treatment strategy during the first 24 hours of resuscitation for sepsis-induced hypotension will reduce 90-day in-hospital mortality.

### 1.4 Study Design

Study Design: Multicenter, prospective, phase 3 randomized non-blinded interventional trial of fluid treatment strategies in the first 24 hours for patients with sepsis-induced hypotension.

1. We will emphasize early screening and protocol initiation, and enroll a maximum of 2320 patients with suspected sepsis-induced hypotension.
  - ✓ All patients will receive at least 1 liter of fluids prior to meeting study inclusion criteria (and no more than 3 liters prior to randomization).
  - ✓ Patients will be enrolled within 4 hours of meeting study inclusion criteria
  - ✓ Any type of isotonic crystalloid (normal saline, ringers lactate, or a balanced solution such as plasmalyte) is permitted.
2. Restrictive Fluids (Early Vasopressors) Group
  - ✓ Norepinephrine will be used as preferred vasopressor and titrated to achieve mean arterial pressure (MAP) between 65 mmHg and 75 mmHg
  - ✓ “Rescue fluids” may be administered as 500ml boluses if predefined rescue criteria are met
3. Liberal Fluids (Fluids First) Group (See Protocol Schema Appendix A)
  - ✓ Additional 2 liter intravenous fluid bolus upon enrollment
  - ✓ Administer 500ml fluid boluses for fluid triggers until 5 liters administered or development of clinical signs of acute volume overload develop
  - ✓ “Rescue vasopressors” may be administered after 5 liters of fluid, for development of acute volume overload, or if other predefined rescue criteria are met

4. Other care
  - ✓ Other elements of care (e.g. antibiotics, ventilation strategies, etc.) will be recommended to reflect current “best-practice” where feasible and appropriate

### 1.5 Inclusion Criteria

1. Age  $\geq$  18 years
2. A suspected or confirmed infection (broadly defined as administration or planned administration of antibiotics)
3. Sepsis-induced hypotension defined as systolic blood pressure  $<$  100 mmHg or MAP  $<$  65 mmHg after a minimum of at least 1 liter of fluid (\*Fluids inclusive of pre-hospital fluids; blood pressure must be below any known or reported pre-morbid baseline).

### 1.6 Exclusion Criteria

1. More than 4 hours elapsed since meeting inclusion criteria or 24 hours elapsed since admission to the hospital
2. Patient already received 3 liters of intravenous fluid (includes prehospital volumes)
3. Unable to obtain informed consent
4. Known pregnancy
5. Hypotension suspected to be due to non-sepsis cause (e.g. hemorrhagic shock)
6. Blood pressure is at known or reported baseline level
7. Severe Volume Depletion from an acute condition other than sepsis.  
In the judgment of the treating physician, the patient has an acute condition other than sepsis causing (or indicative) of \*severe volume depletion;  
**Examples include:** Diabetic ketoacidosis, high volume vomiting or diarrhea, hypersomolar hyperglycemic state, and nonexertional hyperthermia (heat stroke); severe is defined by the need for substantial intravenous fluid administration as part of routine clinical care
8. Pulmonary edema or clinical signs of new fluid overload (e.g. bilateral crackles, new oxygen requirement, new peripheral edema, fluid overload on chest x-ray)
9. Treating physician unwilling to give additional fluids as directed by the liberal protocol
10. Treating physician unwilling to use vasopressors as directed by the restrictive protocol.
11. Current or imminent decision to withhold most/all life-sustaining treatment; this **does not** exclude those patients committed to full support except cardiopulmonary resuscitation
12. Immediate surgical intervention planned such that study procedures could not be followed
13. Prior enrollment in this study

### 1.7 Randomization and Initiation Time Window

All patients must be enrolled and randomized within 4 hours of meeting inclusion criteria. Patients may become eligible in the ED, hospital ward, or ICU.

## 1.8 Primary Endpoint

The primary outcome is all-cause mortality prior to discharge home before day 90.

## 1.9 Secondary Endpoints

1. 28-day organ support free days (alive and without mechanical ventilation, new renal replacement or vasopressors; vasopressors prior to 48 hours excluded)
2. 28-day ventilator free days
3. 28-day renal replacement free days (new renal replacement therapy)
4. 28-day vasopressor free days (vasopressors prior to 48 hours excluded)
5. 28-day ICU free days
6. 28-day hospital free days to discharge home
7. Initiation of mechanical ventilation to day 28
8. Initiation of renal replacement therapy to day 28
9. Change in creatinine-based KDIGO stage between baseline and 72 hours
10. Change in SOFA score between baseline and 72 hours
11. 90-day all-cause mortality
12. Development of ARDS within 7 days
13. New onset atrial or ventricular arrhythmia to day 28
14. Additional secondary safety endpoints:
  - a. New intubation through day seven
  - b. New mechanical ventilation through day seven
  - c. Ventricular arrhythmias in first 24 hours
  - d. New renal replacement therapy through day seven
  - e. New ARDS through day seven
  - f. ICU admission through day seven
  - g. Central venous line insertion through day three
  - h. Vasopressor infusion through peripheral venous catheter
  - i. Line complications of central venous catheter placement
  - j. Line complications
  - k. More than three line complications among patients with a line complication
  - l. Site extravasation to day 28 from peripheral venous catheter infusion
  - m. New ventilation and oxygen use in first 24 hours
  - n. Adverse events

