1.2 Definitions

Adverse Event: Any untoward medical occurrence associated with the use of a drug or a study procedure, whether or not considered drug related.

Adverse reaction: An adverse reaction means any adverse event caused by a study intervention. An adverse reaction is a subset of all suspected adverse reactions where there is a reason to conclude that the study intervention caused the event.

Assisted Ventilation (or Assisted Breathing): any level of ventilatory support at pressures higher than the unassisted breathing thresholds.

Home: Level of residence or health care facility where the patient was residing prior to hospital admission.

Intention to Treat (ITT): All eligible and consented patients who undergo randomization will be included in the ITT cohort for the purposes of analyzing the primary and secondary study outcomes.

Invasive Mechanical Ventilation: Assisted ventilation delivered by a nasotracheal, orotracheal, or tracheostomy tube.

Legally Authorized Representative: An individual, judicial, or other body authorized under applicable law to consent on behalf of a prospective patient to the patient's participation in the clinical study.

Mortality prior to discharge home before day 90: This primary outcome includes deaths from all causes following randomization in any health care facility prior to discharge home until study day 90. Study subjects still in a health care facility at study day 91 are considered alive for this endpoint.

Funding: National Institutes of Health (National Heart Lung and Blood Institute)

SAEs: Serious Adverse Events Adverse events that are serious and unexpected and have a reasonable possibility that the event was due to a study procedure

Sponsor: The Clinical Coordinating Center at Massachusetts General Hospital

Study day: The day of randomization is study day zero. The next day is study day one etc.

Study hospital: Defined as the hospital where the patient was randomized and enrolled.

Study withdrawal: Defined as permanent withdrawal from study before completion of study activities. If a patient or surrogate requests withdrawal from the study the clinician should seek explicit permission to continue data collection.

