11.1 Potential Risks to Subjects

Risk of Fluid Administration: Patients in the liberal fluid protocol may receive additional intravenous fluids. This carries the potential risk of fluid overload, including acute congestive heart failure, breathing difficulties, and increased peripheral edema.

Risk of Vasopressor Administration: Patients in the restrictive protocol may receive early or additional vasopressors based on the treatment assignment. The potential risks of early vasopressors include cardiac ischemia, cardiac dysrhythmias, bowel ischemia, or limb ischemia.

Risks of Blood Draws: All patients will have blood drawn for research purposes. Many patients will have invasive lines placed for clinical purposes, where the risk of blood draws are extremely low, as blood can usually be easily obtained from these lines. In cases where an invasive line is not present, the risks of drawing blood are uncommon and include bleeding and bruising. Commonly, drawing blood is painful, and rarely, drawing blood can lead to infections at the site of the blood draw.

Risk of Line Placement: Patients with hypotension will often have central venous access placed to increase venous access in the anticipation of the need for reliable and increased access for fluid, medication, and vasopressor administration. However, if restoration of blood pressure occurs without needing vasopressor medications, clinicians may decide to not place central venous access. Additionally, clinicians may opt to use peripheral venous access to administer vasopressors. The restrictive fluids protocol is intended to facilitate an increase in the utilization of vasopressors; thus, this practice may lead to an increase in the placement of central venous catheters. The decision to place a central venous line will be left to the treating and/or study clinician. It is possible that additional central venous catheters will be placed in the fluid restrictive group. The risks of central venous access include infection, pneumothorax (punctured lung), and vessel injury, inclusive of inadvertent arterial cannulation.

Peripheral Vasopressor Utilization: Peripheral vasopressor administration is permitted in this protocol. The risk of peripheral vasopressors utilization is extravasation and soft-tissue toxicity/injury if extravasation occurs.

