13.1 Safety Monitoring

Assuring patient safety is an essential component of this protocol. Each participating investigator has primary responsibility for the safety of the individual participants under his or her care. The Investigators will determine daily if any adverse events occur during the period from enrollment through **study day 6** (five days after completion of the study fluid protocol) or Hospital discharge, whichever occurs first.

The following adverse events will be collected in the adverse event case report forms:

- Serious adverse events
- Non-serious adverse events that are considered by the investigator to be related to study procedures or of uncertain relationship (Appendix G)

A clinical trial adverse event is any untoward medical event associated with study procedures, whether or not it is considered related to the study procedures.

After randomization, adverse events must be evaluated by the investigator. If the adverse event is judged to be reportable, as outlined above, then the investigator will report to the CCC their assessment of the potential relatedness of each adverse event to protocol procedure via electronic data entry. Investigators will assess if there is a reasonable possibility that the study procedure caused the event, based on the criteria outlined in Appendix G. Investigators will also

consider if the event is unanticipated or unexplained given the patient's clinical course, previous medical conditions, and concomitant medications.

Determining whether a treatment is causally related to the development of increased oxygen requirements is a challenge, as it is difficult for a clinician to reliably discern hydrostatic from non-hydrostatic pulmonary edema. Furthermore, increased hypoxia and/or need for additional respiratory support may be due to disease progression (eg early phases of ARDS) or a fluid bolus and this is also difficult to discern. We will not consider the study endpoints of use of high-flow nasal cannula, non-invasive ventilation, or endotracheal intubation as AEs unless the events are judged by the investigator to be related to study procedures (see Appendix G2).

If a patient's treatment is discontinued as a result of an adverse event, study site personnel must report the circumstances and data leading to discontinuation of treatment in the adverse event case report forms.

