### Secondary Outcomes

Continuous secondary outcomes will be compared between treatment groups using a t-test.

Categorical secondary outcomes will be compared between treatment groups using a Chi-square or Fisher's exact test as appropriate to the sparseness of the data.

The analysis is intention to treat and significance testing will be two-tailed at  $\alpha = 0.05$  with no adjustment made for multiple comparisons.

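### Safety endpoint 14k compares the arms only among patients who already had a line complication, so it is not an intention-to-treat comparison and can point the other way from the rate per randomised patient

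*SAP*

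**What the plan says.** SAP section 1.9 groups a set of additional safety endpoints under item 14 of the secondary endpoints. Item 14i is "Line complications of central venous catheter placement", item 14j is line complications without further qualification, and item 14k is "More than three line complications among patients with a line complication". Of these three, only 14k is worded with a restricted denominator.

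SAP section 5 (Secondary Outcomes) compares categorical secondary outcomes by a chi-square or Fisher's exact test, at 0.05 and without multiplicity adjustment. It adds: "The analysis is intention to treat and significance testing will be two-tailed". Protocol 1.2 states what that means here: eligible and consented "patients who undergo randomization will be included in the ITT cohort for the purposes of analyzing the primary and secondary study outcomes".

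On whether treatment can affect lines, Protocol 11.1 says: "It is possible that additional central venous catheters will be placed in the fluid restrictive group". It also names catheter injury and infection, and extravasation from peripheral vasopressors, as risks.

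**The concern.** Having a line complication is itself a harm that can follow from the assigned strategy. Once the comparison is limited to patients who had one, randomisation no longer protects it: the two subsets may differ in size and in kind because of the treatment. Extra patients with one, two or three complications enlarge an arm's denominator and lower its 14k rate, although nobody in that arm has been spared anything.

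Two things are at stake. The label is wrong, because a test in this subset is not the intention-to-treat comparison that the SAP states. The direction is also unreliable, because the arm with more line harm can show the lower 14k figure. 14k is the only listed endpoint about repeated line complications, so a reader who wants to know whether these are commoner under one strategy has no other listed result to use.

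**Working it through.** **Inputs.** The maximum sample size is 2,320, randomised 1:1 (Protocol 9.1, SAP 1.11), so 2,320/2 = 1,160 per arm. The documents give no line-complication rates; every rate below is an assumption.

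**The plan's own figure.** For 15% v 10.5%, two-sided 0.05 and 90% power, n per arm = [1.96·√(2·0.1275·0.8725) + 1.2816·√(0.15·0.85 + 0.105·0.895)]² / 0.045² = 1,153, or 2,306 in total. That is within 1% of 2,320, and power at 1,160 per arm is 0.902. This figure serves only to fix the randomised denominator.

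**Population.** Protocol 1.2 takes all randomised patients for secondary outcomes; 14k takes those with at least one line complication. The mismatch is in the text and needs no assumed numbers.

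**Relation between the two scales.** P(more than 3) = P(any) × P(more than 3 | any). Taking restrictive over liberal, the per-randomised ratio is the ratio of any-complication rates times the 14k ratio. The two scales point in opposite directions when the 14k ratio is below 1 and the any-complication ratio exceeds 1/(14k ratio). For a 14k ratio of 0.75 the threshold is 1/0.75 = 1.33.

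**Assumed rates, liberal v restrictive:**

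| Any complication | 14k as written | 14k ratio | More than 3, per randomised | Ratio |
|---|---|---|---|---|
| 2% v 2.5% | 20% v 15% | 0.75 | 0.40% v 0.375% | 0.94 |
| 2% v 3% | 20% v 15% | 0.75 | 0.40% v 0.45% | 1.12 |
| 2% v 4% | 20% v 15% | 0.75 | 0.40% v 0.60% | 1.5 |
| 2% v 6% | 20% v 15% | 0.75 | 0.40% v 0.90% | 2.25 |
| 5% v 10% | 20% v 15% | 0.75 | 1.0% v 1.5% | 1.5 |
| 2% v 4% | 20% v 10% | 0.50 | 0.40% v 0.40% | 1.0 |
| 2% v 6% | 20% v 6.7% | 0.33 | 0.40% v 0.40% | 1.0 |

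The first row lies below the threshold and does not reverse. The next four do. In the last two, the restrictive arm only adds patients with three or fewer complications. For 2% v 4% the expected counts are 0.02 × 1,160 = 23.2 and 0.04 × 1,160 = 46.4 patients with any complication, and 0.004 × 1,160 = 4.64 in each arm with more than three. So 14k is 4.64/23.2 = 20% v 4.64/46.4 = 10%, while the per-randomised difference is zero.

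**What the planned test would do in those last two rows.** With subset sizes fixed at 23 v 46 and true proportions 20% v 10%, exact binomial enumeration gives a significant result in favour of restrictive about 16% of the time by Fisher's test and 21% by the uncorrected chi-square. At 23 v 70 and 20% v 6.7% the figures are 39% and 48%. A two-sided 0.05 test should favour a given arm at most about 2.5% of the time when there is no difference.

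**The case against.** The strongest objection is that 14k will not be read alone. Item 14j sets no subset, and on the same assumed counts it would show the harm plainly: 23 v 46 of 1,160 gives a two-sided Fisher p of about 0.007, and 23 v 70 gives p below 0.001. Items 14g to 14i add line insertion, peripheral infusion and catheter complications. The 14k numerator over arm size also gives the per-randomised rate directly, so no information is lost. This stands, and it limits the weight of the point. It does not repair 14k, because 14j cannot say whether repeated complications are commoner per patient assigned.

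Second, the rates are invented, and a reversal is possible rather than shown to be likely. This also stands. A reader might infer that the protocol predicts more lines in the restrictive arm; Protocol 11.1 speaks only of a possibility. It also notes that hypotensive patients often receive central access anyway and that vasopressors may be given peripherally.

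Third, the SAP's closing Null Hypothesis paragraph warns about outcomes defined only in patients still on study. It attributes the difficulty to differential recovery and survival, not to a harm used as a denominator. Its Type I assurance applies only if treatment affects no patient in any way. That does not cover a strategy that changes line use.

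Finally, a reader might infer a data gap for item 14l, "Site extravasation to day 28 from peripheral venous catheter infusion", because Protocol 13.1 has investigators "determine daily if any adverse events occur during the period from enrollment through" study day 6, and Protocol 7.2, 7.3 and Appendix F name no extravasation item. The documents do not support that. Those lists are not exhaustive: arrhythmia to day 28 is a protocol secondary outcome and is missing from them too. Protocol section 8 has the DSMB reviewing central line complications, which the lists also omit. The day 6 limit governs adverse event determination, and 14l is listed separately from adverse events (14n). No change to 14l follows.

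**Conclusion.** The point holds for 14k and is minor. As worded, 14k is not an intention-to-treat comparison under the protocol's own definition, and this conclusion rests on the text alone. That its direction can differ from the per-randomised comparison follows from the algebra, once the any-complication rates differ enough between arms. How far it would differ is unknown: under the assumed rates, a 14k ratio of 0.75 in favour of restrictive goes with per-randomised ratios from 0.94 to 2.25, and 20% v 10% can appear when the true per-randomised difference is zero.

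A reader might go further and infer that the SAP would make the more harmful strategy look safer on lines overall. It would not, because 14j would show an excess of patients with any complication. The primary outcome, sample size and stopping rules are unaffected.

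**What to change.** Reword 14k in SAP section 1.9 as the proportion of all randomised patients in each arm with more than three line complications, compared with the same test as the other categorical secondary outcomes. Report the share among patients with any line complication beside it as description, without a p-value, and show 14j in the same table.

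This changes SAP wording only and needs no new data. The cost is precision relative to a rare event. At an assumed 0.4% in each arm, the standard error of the difference is √(2 × 0.004 × 0.996 / 1,160) = 0.26 percentage points, so the 95% interval is about ±0.51 points, wider than the rate itself. With about five events per arm, an exact method would be preferable to this normal approximation.

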## 1.10 Process of Care Metrics

**Process of Care Metrics:** We will assess whether the proposed intervention has effectively altered care as intended by measuring:

1. Total intravenous fluids administered over initial 6 hours
2. Total intravenous fluids administered over initial 24 hours
3. Proportion receiving vasopressors and timing of vasopressor initiation within 24-hour study period

4. Total fluids administered prior to initiation of vasopressors

### **1.11 Sample Size/Interim Monitoring**

1. Randomization 1:1; two-sided alpha 0.05.  
A total of 2320 patients are needed to detect a 4.5% absolute mortality difference between treatment groups with 90% power assuming 15% mortality in the liberal fluids group. The principal analysis will be intent-to-treat, based upon randomization assignment.
2. There will be a protocol feasibility assessment phase at the approximately 100-patient mark, and then after approximately 100 enrolled patients are available after any protocol changes for 2 more evaluation assessments. Aggregate data blinded to outcomes will be used to assess patient accrual, treatment protocol compliance, and separation of intravenous fluid and/or vasopressor administration. Protocol adjustments may be made at each of these patient marks to optimize the protocol. The study may be halted during the feasibility assessment phase for failure to meet pre-specified stopping guidelines
3. Trial progress will be evaluated by an independent Data and Safety Monitoring Board (DSMB) to determine whether the study should stop for superiority of either the liberal or restrictive fluid strategies; or, for projected trial futility. (See Appendix B) There will be two interim analyses and a final analysis conducted when approximately each successive 1/3 of the patients have been enrolled.

## **2. Endpoints**

### **2.1 Primary Outcome**

The primary outcome is all-cause mortality prior to discharge home before day 90. "Home" is defined as a patient's place of residence prior to enrollment. Thus, if a patient is discharged to a location that is different from the place of residence prior to enrollment (e.g. rehabilitation facility or hospice) then the patient will be followed until they return to their original location, 90 days, or death, whichever comes first.

